Body weight and height			X		X	X		X		Baseline height is required. Weight should be measured at baseline (predose C1D1), C1D15, D1 of each subsequent cycle, and at EOT.
Ophthalmic examination including retinal examination with OCT	X					X		X		Ophthalmic examination should be performed by an ophthalmologist during screening, between C2D1 to D7, then every 3 cycles, and EOT. See Section 8.2.7 for details.
Head MRI	X									Required within 4 weeks of C1D1 for participants with previous history of brain metastases. See Section 5.2, E03 .
Pregnancy test (WOCBP only)		X	X			X		X		For females of childbearing potential (including tubal ligation), perform a blood pregnancy test at screening and a urine/blood pregnancy test predose on D1 of each cycle, as well as at the EOT. See Section 10.2 for details.

Procedure (Part-1 and Part-4)	Screening ^a		Cycle 1 (21-day cycle)			Cycles 2+ (21-day cycle)		EOT (within 30 ±5d of last dose) ^b	LTFU (every 3 months ±2 wks) ^c	Notes E/D=Early Discontinuation
Day	-1 to -28	-1 to -14	1	8 (±1 d)	15 (±1 d)	1 (±2 d)	15 (±2 d)			
Coagulation tests		X	X			C3D1 then QO cycle		X		C1D1 hematology, chemistry, and coagulation samples are not required, if they were obtained within the previous 72 hours as part of screening. Participants receiving anticoagulation in which PT/aPTT (or partial thromboplastin time [PTT]) may be affected, should undergo additional monitoring on D1 at least every other cycle starting with C3D1 and then at EOT. Additional testing may be performed as clinically indicated. See Section 10.2 for details.
Laboratory assessments (including liver chemistries)		X	X	X	X	X	X	X		C1D1 hematology, chemistry, and coagulation samples are not required, if they were obtained within the previous 72 hours as part of screening. Testing must be performed and reviewed before dosing on C1D1. See Section 10.2 for details. C2+Day 15 laboratory assessments could be done remotely if needed and after discussion with the Study Medical Manager.
12-lead ECG		X	X		X	C3D1 then QO cycle		X		A single pre dose ECG should be obtained on C1D1 and C1D15 and then D1 of every 2 cycles starting at C3 (eg, C3D1, C5D1, etc) and at EOT See Section 8.2.4 .
Hepatitis B and C	X									See Section 10.2 .
Urinalysis		X	X			X				See Section 10.2 .

Procedure (Part-1 and Part-4)	Screening ^a		Cycle 1 (21-day cycle)			Cycles 2+ (21-day cycle)		EOT (within 30 ±5d of last dose) ^b	LTFU (every 3 months ±2 wks) ^c	Notes E/D=Early Discontinuation

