Medical history	X								Prior cancer history includes: (i) date of diagnosis, (ii) staging, (iii) all previous therapies (ie, chemotherapy, immunotherapy, biologic or targeted agents, experimental therapies, radiotherapy, and surgery), (iv) previous therapy details (ie, regimen, start and stop dates), (v) best response for each regimen, and (vi) date of relapse or disease progression.
Past and current medical conditions	X								
Documentation of tumor genotypic mutations	X								
ECOG performance status		X	X			X		X	ECOG performance status to be assessed at screening, C1D1, and D1 of each subsequent cycle beginning at C2, and at EOT.

Procedure (Part-3)	Screening ^a		Cycle 1 (21-day cycle)			Cycles 2+ (21-day cycle)		EOT (within 30 ±5d of last dose) ^b	Notes
Day	-1 to -28	-1 to -14	1	8 (±1 d)	15 (±1 d)	1 (±2 d)	15 (±2 d)		
Vital signs		X	X	X	X	X	X	X	Vital signs should be taken prior to administration of study intervention. See protocol for details.
Body weight and height			X		X	X		X	Baseline height is required. Weight should be measured at baseline (predose C1D1), C1D15, D1 of each subsequent cycle, and at EOT.
Ophthalmic examination including retinal examination with OCT	X					X		X	Ophthalmic examination should be performed by an ophthalmologist during screening, and EOT. Unscheduled ophthalmology consultation recommended per Investigator's discretion as clinically indicated
Head MRI	X								Required within 4 weeks of C1D1 for participants with previous history of brain metastases.
Pregnancy test (WOCBP only)		X	X			X		X	For females of childbearing potential (including tubal ligation), perform a blood pregnancy test at screening and a urine/blood pregnancy test predose on D1 of each cycle, as well as at the EOT.
Coagulation tests		X	X			C3D1 then QO cycle		X	Additional testing may be performed as clinically indicated.
Laboratory assessments (including liver chemistries)		X	X	X	X	X	X	X	C1D1 hematology, chemistry, and coagulation samples are not required, if they were obtained within the previous 72 hours as part of screening. Testing must be performed and reviewed before dosing on C1D1. C2+Day 15 laboratory assessments could be done remotely if needed and after discussion with the Study Medical Manager.

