12-lead ECG		X	X		X	C3D1 then QO cycle		X	A single pre dose ECG should be obtained on C1D1 and C1D15 and then D1 of every 2 cycles starting at C3 (eg, C3D1, C5D1, etc) and at EOT. Unscheduled ECGs to be obtained in case of signs and symptoms, and as per Investigator's assessment.

Procedure (Part-3)	Screening ^a		Cycle 1 (21-day cycle)			Cycles 2+ (21-day cycle)		EOT (within 30 ±5d of last dose) ^b	Notes
Day	-1 to -28	-1 to -14	1	8 (±1 d)	15 (±1 d)	1 (±2 d)	15 (±2 d)		
Hepatitis B and C	X								
Urinalysis		X	X			X			
ECHO/MUGA	X					C2 D1-7 then Q3 cycle		X	ECHO is the preferred methodology to measure LVEF. MUGA scan may be used if ECHO is not available or not technically feasible. However, the same methodology should be used throughout the study. Assessments should be performed during screening, C2 D1-7, every 3 cycles thereafter, and EOT, and as clinically indicated.
CPK (total and MB isoenzyme)			X			X		X	CPK levels should be obtained at C1D1, D1 of each cycle, EOT and as clinically indicated.
Tumor assessments									
CT/MRI scan	X					Every 6 weeks (+/- 7 days)		X	RECIST tumor response assessment will be performed at the time of each scan.
PDy and biomarker assessments									
Archival tumor tissue	X								In case fresh tumor biopsy cannot be collected as required, archival tumor tissue should be obtained from biopsies done within 6 months to be submitted between screening and C2D15.
Fresh tumor biopsy			X		X			X	Fresh tumor biopsy is optional in dose escalation (Part-3A). Fresh tumor biopsy is required in dose expansion (Part-3B). The on-treatment and EOT biopsies are optional, on-treatment biopsy may be obtained at C1D15 with a window of +7 days. On treatment and EOT biopsy should be collected from the same lesion as baseline.
ctDNA biomarker			See Table 10 below						
Study intervention									
SAR442720 dosing			Continuous dosing (twice weekly)						SAR442720 is administrated orally at home or at the hospital.

Procedure (Part-3)	Screening ^a		Cycle 1 (21-day cycle)			Cycles 2+ (21-day cycle)		EOT (within 30 ±5d of last dose) ^b	Notes
Day	-1 to -28	-1 to -14	1	8 (±1 d)	15 (±1 d)	1 (±2 d)	15 (±2 d)		
Adagrasib			Continuous dosing (twice daily)						Adagrasib is administrated orally at home or at the hospital.
Assessment and documentation of study compliance			←=====→						Participants should be instructed to bring their pills and diary to every visit.
AE review		X	←=====→					X	Predose on C1D1 also See Section 8.3

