4.1.1 Dose-limiting toxicity criteria (Part-1 and Part-3A)

Potential DLTs are defined as all AEs specified below occurring during the first cycle of treatment considered by the investigator to be related to study treatment, unless due to disease progression or to a cause obviously unrelated to IMP.

- Grade ≥ 4 AEs.
- Grade 3 neutropenia lasting > 7 days or febrile neutropenia.
- Grade 3 thrombocytopenia with clinically significant bleeding.
- Any Grade ≥ 3 immune-related AEs (irAE) (Part-1, 2, and 4 only).

An irAE can occur shortly after the first dose or several months after the last dose of treatment. All AEs of unknown etiology associated with drug exposure should be evaluated to determine possible immune etiology. If an irAE is suspected, efforts should be made to rule out neoplastic, infectious, metabolic, toxin or other etiologic causes prior to labeling an AE as an irAE.

- Grade 3 nonhematologic AEs, including rash, nausea/vomiting, hypertension, diarrhea, retinopathy, or blurred vision that remain uncontrolled (does not resolve to \leq Grade 2) for > 72 hours despite maximal supportive care. Electrolyte abnormalities or Grade 3 asymptomatic creatine phosphokinase (CPK) or gamma-glutamyl transferase (GGT) elevations that are corrected within 72 hours will not be considered DLTs.
- Grade 3AST, ALT, and/or total bilirubin elevations that persist > 5 days.

- Concurrent elevation of AST or ALT $>3 \times$ upper limit of normal (ULN) and total bilirubin $>2 \times$ ULN or international normalized ratio (INR) >1.5 in the absence of cholestasis and other causes (eg, viral hepatitis, other pre-existing or acute liver disease, or another drug capable of the observed injury), which may indicate severe drug-induced liver injury (possible Hy's law case).
- Grade 3 QTcF (defined as QT interval corrected using Fridericia's formula [QTcF] >450 msec or change from baseline of QTcF >50 msec) prolongation.
- Retinal vein occlusion (RVO) any grade
- Toxicity related to IMP leading to 50% or less dose intensity of SAR442720 (eg, miss ≥ 3 doses) and/or delay in initiation of Cycle 2 dosing of pembrolizumab by >15 days, in the absence of recovery to baseline or Grade ≤ 1 (except for alopecia, vitiligo, fatigue and thyroiditis) AE. Toxicity resulting in the inability to deliver at least 66.7% of the dose of adagrasib (Part-3A) as intended for the duration of the cycle.

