- An absolute decrease in LVEF of 20 percentage points or greater from the baseline value to a value that is below the institutional lower limit of normal (LLN) value, OR symptomatic systolic dysfunction with LVEF decrease from baseline $\geq 10\%$ and/or below LLN.

At the end of Cycle 1, each participant must be assessed by the Investigator to determine if he or she experienced a DLT. This information must be recorded on the appropriate electronic case report forms (eCRFs), and an electronic DLT notification (either DLT or not) will be sent to the Sponsor, before a subsequent cycle may begin.

Potential and IMP related DLTs will be considered as AESIs. As such, Investigators are required to report them to the Sponsor within 24 hours of the Investigator becoming aware of each AE. The Investigator will attach the DLT-specific case report form (CRF) page to the transmitted DLT/AESI form or will complete the specific DLT form in the eCRF.

The reported potential DLTs will be reviewed by the Sponsor and recruiting Investigators in order to determine their relationship to the IMP and confirm them as DLTs.

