9.4.1 General considerations

All baselines are defined as the last assessment prior to the first dose unless specified otherwise. The MTD recommendation will be based on the DLT-evaluable population Cycle 1 data only. All safety and efficacy analyses will be based on the safety population unless otherwise specified. The Part-1 and Part-3A analyses will be performed separately by different dose levels unless specified otherwise. The Part-2 and Part-3B analyses will be presented separately, with Part-2 presented by different cohorts and overall, and Part-3B as a single cohort.

The analysis period will be divided into 3 segments:

- The pre-treatment period is defined as the time from when the participants give informed consent to the first administration of the IMP.
- The treatment period (ie, treatment-emergent period) is defined as the time from the first administration of IMP up to 30 days after the last administration of IMP.
- The post-treatment period is defined as the time from the 31 days after the last administration of IMP.

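### The scheduled LVEF and eye tests come after the Cycle 1 DLT call, so silent LVEF falls below LLN and silent RVO would normally be missing from the DLT count that drives mTPI2 (operative for Part-3A)

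*Protocol*

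**What the plan says.** Protocol Section 4.1.1 ties the DLT definition to time: "Potential DLTs are defined as all AEs specified below occurring during the first cycle of treatment". The criteria include "An absolute decrease in LVEF of 20 percentage points or greater from the baseline value" to below the institutional LLN, with no symptom required. Symptomatic systolic dysfunction with a smaller fall is a separate alternative. RVO of any grade is also listed. Section 4.1 sets the observation period at one 21-day cycle.

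At the end of Cycle 1 the investigator decides whether there was a DLT, and the notice "will be sent to the Sponsor, before a subsequent cycle may begin". Under Section 4.2.1 the escalation decision follows once the last DLT-evaluable participant in the cohort has completed Cycle 1.

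The schedules of activities (Section 1.3) time the tests as follows:
- ECHO/MUGA, Tables 2 and 4 (Part-1 and Part-3): "Assessments should be performed during screening, C2 D1-7, every 3 cycles thereafter, and EOT, and as clinically indicated".
- Eye examination with OCT, Table 2 (Part-1): "Ophthalmic examination should be performed by an ophthalmologist during screening, between C2D1 to D7, then every 3 cycles, and EOT".
- Eye examination with OCT, Table 4 (Part-3), note: "Ophthalmic examination should be performed by an ophthalmologist during screening, and EOT", plus unscheduled consultation when indicated. The grid in the same row also has a mark under Cycles 2+ Day 1.

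On the use of these data, Section 9.4.1 says: "The MTD recommendation will be based on the DLT-evaluable population Cycle 1 data only". SAP Section 4.1 agrees, and so does the Part-1 text below Table 13. The Synopsis and other Part-1 and Part-3A text in Section 4.1 instead bring all adverse events during treatment into the determination of both MTD and RP2D, except those due to progression or clearly unrelated.

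**The concern.** Cycle 1 DLT incidence is a primary endpoint of Part-1 and Part-3A (Section 3, Table 12) and is the count that mTPI2 works on. For two of its components, the planned measurement comes after the endpoint has been declared. A participant with an asymptomatic qualifying LVEF fall, or an RVO without visual symptoms, would ordinarily be signed off as DLT-evaluable without a DLT. The next cohort could open before the scheduled test is done.

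This matters most in Part-3A. That part tests a new combination in which Section 2.3.1.5 expects SAR442720 exposure to rise by up to 2-fold. The protocol already treats these organs as areas of risk: E 06 and E 07 exclude participants with retinal risk factors or reduced LVEF.

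**Working it through.** **1. The DLT window.** The planned Cycle 1 doses in Section 9.3 reproduce the stated length.
- SAR442720: 6 doses at 2 per week, 6/2 × 7 = 21 days.
- Adagrasib: 42 doses at 2 per day, 42/2 = 21 days.

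The window is Days 1-21.

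**2. The first scheduled on-treatment tests.** C2D1 is Day 21 + 1 = 22 and C2D7 is Day 21 + 7 = 28.
- ECHO/MUGA (Part-1 and Part-3) and Part-1 eye examination: Days 22-28, which is 22 − 21 = 1 to 28 − 21 = 7 days after the window closes.
- If the ±2-day window of the Cycles 2+ Day 1 visit is applied, the range becomes Days 20-30. A test at an early C2D1 visit could then fall on Day 20 or 21.
- Part-3 eye examination: nominal Day 22 by the grid (Days 20-24 with the window), or EOT by the note.

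The Cycle 1 visits are Days 1, 8 and 15. The ECHO/MUGA and eye rows have no entry under any of them, so the number of such tests at Cycle 1 visits is 0 in Part-1 and 0 in Part-3A.

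**3. Order of events.** Cycle 1 ends on Day 21. The DLT notice is due before Cycle 2 begins. The scheduled tests nominally follow on Days 22-28. The cohort decision depends on completion of Cycle 1, and nothing ties it to the result of those tests.

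**4. Possible size.** The documents give no rate for silent events, so a range is assumed. The chance of at least one among n participants is 1 − (1 − p)^n.

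| Assumed silent rate p | n = 3 | n = 6 |
|---|---|---|
| 2% | 5.9% | 11.4% |
| 5% | 14.3% | 26.5% |
| 10% | 27.1% | 46.9% |

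One uncounted event changes the observed rate by 1/6 = 17 points in a group of 6, or 1/3 = 33 points in a group of 3.

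The target DLT rate and the mTPI2 boundaries are redacted, so the effect on a particular decision cannot be computed. As an illustration, assume a total true DLT rate t, of which 0, 5 or 10 percentage points are silent and unseen. With q = t minus the silent part, P(at most 1 DLT counted in 6) = (1 − q)^6 + 6q(1 − q)^5.

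| Assumed t | none unseen | 5 points unseen | 10 points unseen |
|---|---|---|---|
| 25% | 53.4% | 65.5% | 77.6% |
| 30% | 42.0% | 53.4% | 65.5% |
| 40% | 23.3% | 31.9% | 42.0% |

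**The case against.** The strongest reply is that the gap is narrow and has other safeguards. Much of that stands.
- ECHO/MUGA and eye examinations can be done earlier when clinically indicated (Tables 2 and 4, Section 8.2.7), and Section 6.6.1.3 calls for immediate consultation for visual changes above Grade 1. Symptomatic events therefore have a route to detection in Cycle 1.
- The retinopathy criterion is Grade 3, uncontrolled for more than 72 hours despite supportive care. That describes an event already under management, so it is not part of this point.
- A 20-point LVEF fall that stays at or above LLN is not a DLT under the asymptomatic limb.
- DLT-type events after Cycle 1 are AESIs (Section 8.3.6), reportable within 24 hours. The Study Committee may also choose a dose below the model's recommendation (Section 4.1.2).
- Among 242 exposed participants, the potential risks listed in Section 2.3.1.1 are edema, diarrhea, anemia and thrombocytopenia, not LVEF or retinal events.

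These safeguards do not put a silent event into the Cycle 1 count or hold the cohort decision for the test. The early visit window helps only incidentally, because the ECHO/MUGA may be done at any time up to C2D7.

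A reader might also cite the criterion on a "delay in initiation of Cycle 2 dosing of pembrolizumab by >15 days" as another example. That is a separate matter. No test is needed to see a dosing delay, Section 4.1.1 frames the DLT as the toxicity leading to it, and pembrolizumab is not given in Part-3A.

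**Conclusion.** The point holds for two event types: an asymptomatic LVEF fall of at least 20 points to below LLN, and an RVO without symptoms. On the nominal schedule neither has a planned test inside the DLT window, so neither would normally enter the Cycle 1 DLT count. How often this would matter is unknown. The probabilities above rest on assumed rates and show only that small cohorts leave little margin.

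Two stronger readings are not supported. A reader might infer that such events are shut out of the MTD altogether. The Synopsis and Section 4.1 bring all on-treatment adverse events into that determination, and the Study Committee has discretion. Because Section 9.4.1, SAP Section 4.1 and the text below Table 13 limit the MTD to Cycle 1 data, the sound conclusion is that the documents conflict on the data basis. A reader might also infer that Part-3 has no on-treatment eye examination. The Table 4 grid marks one, so the finding is a contradiction between grid and note; under either, none is scheduled in Cycle 1.

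Nor does this justify reopening the Part-1 DLT summary. Sections 4.1 and 4.3 show that the Part-1 dose has already been selected.

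**What to change.** For Part-3A, the sponsor should reconcile three sets of passages and choose how to do so:
1. The DLT criteria in Section 4.1.1, the Table 4 timing of the existing ECHO/MUGA and eye examinations, and the timing of DLT sign-off and the cohort decision, so that each DLT criterion can be assessed by a scheduled test before the decision that uses it.
2. The Table 4 ophthalmic grid and its note.
3. The two statements of which data define the MTD: Cycle 1 only (Section 9.4.1, the text below Table 13, SAP Section 4.1) or all on-treatment adverse events (Synopsis, Section 4.1).

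The change is mainly protocol wording. In practice either an existing examination shifts by about a week, with correspondingly less exposure before the test, or a cohort decision waits up to about 7 days. For the Part-3 eye examination, the cost also depends on whether the sponsor confirms the grid or the note.

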4.1.2 Dose escalation

In Part-1 and Part-3A, dose escalation will follow mTPI2 design with a minimum of 3 participants evaluable for DLT in the first cycle. A participant will be considered evaluable for DLT assessment if he/she receives at least 4 out of the 6 planned doses of SAR442720 in the first cycle and completes the DLT observation period or if he/she experiences a DLT in the DLT observation period. A participant who is not DLT-evaluable will be replaced to achieve a minimum of 3 DLT-evaluable participants at the same cohort.

The actual dose selected at each dose escalation decision, and the MTD identified at the conclusion of the dose escalation phase, will be determined by the Study Committee, in agreement with the Sponsor's Study Medical Manager, which may select a dose at or below the model's recommendation and should not select a dose that is suggested to be over toxic by the model. The Study Committee will review the overall safety of all dose levels. More details in the model and its operating characteristics can be found in Appendix 11 ([Section 10.11](#)).

The adaptive dose escalation design is based on the boundaries generated from the mTPI2 design. The dose escalation will stop if the next recommended dose has been collectively evaluated in at least 2 previous escalation cohorts.

It is anticipated that in Part-1 12 to 18 DLT-evaluable participants and in Part-3A 15 to 30 DLT-evaluable participants will be enrolled in the dose escalation. The actual total number of participants required will depend on the number of dose levels evaluated and on the incidence and timing of observed DLTs.

4.2 SCIENTIFIC RATIONALE FOR STUDY DESIGN

The first phase of the study (Part-1) constitutes a Dose Escalation, which has been designed to minimize the number of participants exposed to potentially subtherapeutic doses.

In the Dose Escalation, assessment of safety and tolerability will be the primary endpoints and will be directly measured by the incidence of DLTs, AEs, and SAEs. The dose escalation rationale is provided below in [Section 4.2.1](#).

A mini-expansion cohort of 6 participants will be initiated to further assess the safety, PK, PD, as well as the preliminary anti-tumor activity of SAR442720 and pembrolizumab combination therapy at RP2D.

The Part-2 of this study aims to establish the efficacy of combining the ICI pembrolizumab with the SHP2 inhibitor SAR442720 which may result in an increase in ORR. The goal of combination therapy approaches is to expand the spectrum of patients who respond to cancer immunotherapy and to improve the quality of clinical responses (ie, durable response OS and prolonged PFS) beyond what can be achieved with monotherapy alone. The established anti-tumor activity of PD-1/PD-L1 inhibition as monotherapy in a wide spectrum of cancers coupled with its favorable toxicity profile provides a strong rationale for its use as a backbone for combinatorial strategies.

The design of the study is a non-randomized study where the experimental combination will be assessed in a single cohort for each indication. The ORR will be assessed using RECIST v1.1 for participants with NSCLC. The objective response will be assessed per Investigator in first intention. Central imaging reading may be done retrospectively if significant activity is observed.

Part-3A constitutes a dose escalation study to determine the MTD and RP2D of SAR442720 in combination with adagrasib in participants with NSCLC and KARAS G12C mutations. The starting dose of SAR442720 is 50% of the highest cleared dose in monotherapy and adagrasib starting dose is 2/3 of RP2D for adagrasib. In the dose escalation part, assessment of safety and tolerability will be the primary endpoints and will be directly measured by the incidence of DLTs, AEs, and SAEs.

Part-3B aims to determine the anti-tumor activity of SAR442720 in combination with adagrasib in participants with NSCLC and KARAS G12C mutations, which can result in an increased ORR. The goal of the combination therapy approach is to expand the spectrum of patients who respond to targeted KRAS G12C therapy and to improve the quality of clinical responses (ie, durable response and prolonged PFS) beyond what can be achieved with monotherapy alone.

The design of the study is a non-randomized study in which the experimental combination will be assessed in a single cohort for each indication. The ORR will be assessed using RECIST v1.1. The objective response will be assessed by the Investigator in first intention. Central imaging reading may be done retrospectively if significant activity is observed.

Part-4 aims to assess the impact of formulation and preliminary impact of food on the PK of SAR442720 in combination with pembrolizumab. Part-4 is an open label, non-randomized fixed-sequence study, intending to assess preliminary effect of food on SAR442720 tablet and relative bioavailability of SAR442720 tablets versus capsules in participants with advanced malignancies. The PK of SAR442720 under fasted state will be served as the test treatment of formulation bridging; therefore, both the food effect and formulation effect can be assessed in the same participants, to reduce the number of participants needed.

